6.12.6. Vital Signs and Other Physical Findings

Post-baseline measurements and change from baseline to post-baseline for vital signs and physical characteristics (systolic blood pressure [SBP], diastolic blood pressure [DBP], pulse rate, weight, BMI) at the scheduled visits will be summarized for patients who have both baseline and at least 1 post-baseline result.

The measurements during the treatment period (0 to 26 weeks) will be analyzed by an MMRM model with treatment, baseline value of the response variable, visit, and visit by treatment interaction as fixed factors and patient as the random factor.

The weight measurement during the lead-in period will also be analyzed by an MMRM model with Visit 2 value of the response variable, randomized treatment, visit and treatment-by-visit interaction as fixed factors, and patient as the random factor. The analysis will be conducted on all randomized patients.

An ANCOVA model will also be used for the analysis of the last nonmissing observation (including early discontinuation visit) during the treatment period and during the entire study (up to Visit 801). The ANCOVA models are the same as those used for clinical laboratory measures.

Change from the minimum value during the baseline period to the minimum value during the treatment period (0 to 26 weeks) for vital signs and physical characteristics will be summarized for patients who have both baseline and at least 1 post-baseline result. Baseline will be the minimum of nonmissing observations in the baseline period. The minimum value in the treatment period will be analyzed. Similarly, change from the maximum value during the baseline period to the maximum value during the treatment period (0 to 26 weeks) for vital signs and physical characteristics will be summarized for patients who have both baseline and at least 1 post-baseline result. Baseline will be the maximum of nonmissing observations in the baseline period. The maximum value in the treatment period will be analyzed.

The percentages of patients with treatment-emergent high or low vital signs and weight at any time during the treatment period (0 to 26 weeks) or during the entire study including safety follow-up period will be summarized by treatment group for patients who have both baseline and at least 1 postbaseline measurement. A treatment-emergent high result is defined as a change

from a value less than or equal to the high limit at all baseline visits to a value greater than the high limit at any time that meets the specified change criteria during the treatment period or during the entire study including safety follow-up period. A treatment-emergent low result is defined as a change from a value greater than or equal to the low limit at all baseline visits to a value less than the low limit at any time that meets the specified change criteria during the treatment period or during the entire study including safety follow-up period. Treatment comparison will be based on Fisher's exact test. Table 6.7 will be used to define the low and high limits and change thresholds.

Table 6.7. Categorical Criteria for Abnormal Treatment-Emergent Blood Pressure and Pulse Measurement, and Categorical Criteria for Weight for Adults

Parameter	Low	High
Systolic BP (mm Hg) (Supine or sitting – forearm at heart level)	≤ 90 and decrease from baseline ≥ 20	≥ 140 and increase from baseline ≥ 20
Diastolic BP (mm Hg) (Supine or sitting – forearm at heart level)	≤ 50 and decrease from baseline ≥ 10	≥ 90 and increase from baseline ≥ 10
Pulse (bpm) (Supine or sitting)	< 50 and decrease from baseline ≥ 15	> 100 and increase from baseline ≥ 15
Weight (kg) (Consistent clothing and timing in relationship to meals and voiding)	(Loss) decrease $\geq 7\%$	(Gain) increase $\geq 7\%$

Abbreviations: BP = blood pressure.

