Unless otherwise noted, all tests of treatment effects will be conducted at a 2-sided alpha level of 0.05, and CIs will be calculated at 95%, 2-sided. All tests of interactions between treatment groups and other factors will be conducted at a 2-sided alpha level of 0.10. Countries in similar geographic regions with fewer than 10 patients, based on the all-randomized population, will be pooled to achieve a pooled country of at least 10 patients. All analyses using country in the model will use a pooled country, unless otherwise specified. The final pooling by country and geographic region will be finalized prior to data lock.

A graphical approach for multiple comparisons (Bretz et al. 2011) will be used to strongly control the overall Type I error (2-sided alpha level of 0.05) for testing the treatment effect for the primary and multiplicity adjusted objectives.

Baseline is defined as the last nonmissing measurement at or before the randomization visit (Visit 8) unless otherwise specified.

A restricted maximum likelihood-based, mixed-effect model repeated measures (MMRM) analysis will be used to analyze continuous longitudinal variables. All the longitudinal observations at each scheduled postbaseline visit will be included in the analysis. The model for the analysis of the primary efficacy endpoint of change from baseline in HbA1c will include the fixed class effects of treatment, strata (pooled country, type of basal insulin, and number of prandial doses at entry), visit, and treatment-by-visit interaction, as well as the continuous, fixed covariate of baseline value. For analyses of variables other than HbA1c, the HbA1c stratum ($\leq 8\%$, $> 8\%$) will be included in the model. An unstructured covariance structure will be used to model the within-patient errors. Significance tests will be based on least squares (LS) means and Type III tests. SAS PROC MIXED will be used to perform the analysis. If this analysis fails to converge, the following covariance structures will be tested in order:

- Toeplitz with heterogeneity
- Autoregressive with heterogeneity
- Compound symmetry with heterogeneous variances
- Toeplitz
- Autoregressive
- Compound symmetry without heterogeneous variances

The first covariance structure that converges will be used. The Kenward-Roger approximation will be used to estimate denominator degrees of freedom.

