Continuous safety variables, as well as the change from baseline for these variables, will be analyzed either by MMRM or ANCOVA models. For categorical variables, Fisher's exact test or Pearson's chi-square test will be used to compare treatment groups unless otherwise specified.

The analyses for assessing immunogenicity data will be described in the SAP after being agreed with the FDA on the threshold for determining treatment-emergent antibodies to insulin lispro.

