16. To compare LY900014 and insulin lispro with respect to the impact that diabetes has on the ability to work and perform regular activities as measured by the WPAI-GH	16. Change from baseline in WPAI-GH item scores at Week 26
17. To compare LY900014 and insulin lispro with respect to changes in body weight	17. Change from baseline to Week 26 in weight (kg)
18. To compare LY900014 and insulin lispro with respect to the proportion of patients achieving improvement from baseline HbA1c targets	18. The proportion of patients with shifts in HbA1c to <8% and ≤9%, and >9% from baseline to Week 26
19. To compare LY900014 and insulin lispro with respect to glycemic variability	19. Within-day and between-day glycemic variability measured by the standard deviation and the coefficient of variation of 10-point SMBG profiles

Abbreviations: 1,5-AG = 1,5-Anhydroglucitol; EQ-5D-5L = European Quality of Life – 5 Dimensions 5 Level; EQ-VAS = EuroQol visual analog scale; HbA1c = hemoglobin A1c; ITSQ = Insulin Treatment Satisfaction Questionnaire; MMTT = mixed-meal tolerance test; NIM = noninferiority margin; PPG = postprandial glucose; SMBG = self-monitored blood glucose; T2D = type 2 diabetes; WPAI-GH = Work Productivity and Activity Impairment Questionnaire General Health.

5. Study Design

[figure not shown]

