6.1. General Considerations

Statistical analysis of this study will be the responsibility of Eli Lilly and Company (hereafter Lilly). Any change to the data analysis methods described in the protocol will require an amendment ONLY if it changes a principal feature of the protocol. Any other change to the data analysis methods described in the protocol, and the justification for making the change, will be described in this SAP and/or in the clinical study report (CSR). Additional exploratory analyses will be conducted, as deemed appropriate.

Statistical analyses for Japan are described in [Appendix 2](#). Statistical Analyses for the Maximum Extended Enrollment (MEE) Addendum are described in [Appendix 3](#).

For purposes of analysis, the following populations are defined in [Table 6.1](#):

Table 6.1. Patient Populations

Population	Description
Entered	All patients who give informed consent.
Enrolled	All patients who receive at least 1 dose of open-label insulin lispro in the 8-week lead-in period.
Randomized	All patients who are randomly assigned to study treatment at Visit 8. Treatment group will be defined on the basis of the treatment the patients are assigned.
Safety	All randomized patients who receive at least 1 dose of the randomly assigned investigational product (IP). Treatment group will be defined on the basis of the treatment the patients are assigned.
Completer	Patients included in the randomized population who have completed Week 26 of study treatment without permanent discontinuation of IP. Treatment group will be defined on the basis of the treatment the patients are assigned.
Per Protocol	Patients included in the randomized population who have completed Week 26 of study treatment without permanent discontinuation of IP and without significant protocol deviations through Week 26 that would significantly impact the primary objective. Treatment group will be defined on the basis of the treatment the patients actually receive.

Unless otherwise stated, the efficacy analyses will be conducted on the Randomized Population, and the safety analyses will be conducted on the Safety Population.

The primary analysis is for the treatment period through Week 26.

Unless otherwise noted, all tests of treatment effects will be conducted at a 2-sided alpha level of 0.05, and CIs will be calculated at 95%, 2-sided. All tests of interactions between treatment groups and other factors will be conducted at a 2-sided alpha level of 0.10.

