Total daily basal insulin dose, total daily prandial insulin dose, total insulin dose, and the ratio of prandial insulin dose to total insulin dose during the lead-in period will be summarized by visit for the Randomized Population. The actual and change from Visit 2 values will be compared between treatment groups using an MMRM model including the corresponding dose at Visit 2, treatment, strata (pooled country, type of basal insulin, the number of prandial doses at study entry and HbA1c stratum), visit, treatment-by-visit interaction in the model as fixed factors and patient as a random factor. Doses will be summarized in U and U/kg. Basal insulin dose will be summarized independently for glargine and degludec as well as combined.

Up to 3 OAMs (metformin, dipeptidyl peptidase-4 inhibitor [DPP-4] inhibitor, sodium-glucose co-transporter 2 [SGLT2] inhibitor, sulfonylurea, meglitinide and alpha-glucoside inhibitor) are allowed prior to the study, and up to 2 OAMs (metformin and SGLT2 inhibitor) are allowed during the lead-in and treatment periods. The proportion of patients who were treated with OAMs (by class of OAM) at each visit will be summarized and compared between treatment groups using Fisher's exact test. The number of OAMs per patient will also be summarized by treatment and by period: lead-in period (Visit 2 to Visit 8) and treatment period (Visit 8 to Visit 18).

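### The SAP models for weight, vital signs, antibody binding and lead-in insulin dose name patient as a random factor and no covariance structure, which read literally conflicts with the protocol's unstructured covariance

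*SAP*

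**What the plan says.** Protocol 10.3.1 sets up the trial's general repeated-measures model: a REML-based "mixed-effect model repeated measures (MMRM) analysis will be used to analyze continuous longitudinal variables". It then fixes the errors: "An unstructured covariance structure will be used to model the within-patient errors". If that model fails to converge, six simpler structures are tried in order, and homogeneous compound symmetry is the last of them. Kenward-Roger degrees of freedom are used.

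Protocol 10.3.4 says of safety data: "Continuous safety variables, as well as the change from baseline for these variables, will be analyzed either by MMRM or ANCOVA models". It names no covariance there. Protocol 10.3.3.3 sends continuous tertiary and exploratory variables to the 10.3.1 models and leaves analysis details to the SAP. Weight change to Week 26 is objective 17, listed as tertiary/exploratory in both documents.

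SAP 6.11.1 repeats the unstructured covariance and its fallback list for HbA1c, and 6.11.5 carries that model over to several secondary endpoints. SAP 6.12.6 does not refer back to it. Its treatment-period model for weight, BMI, blood pressure and pulse ends with "visit, and visit by treatment interaction as fixed factors and patient as the random factor", and its lead-in weight model with "treatment-by-visit interaction as fixed factors, and patient as the random factor". SAP 6.12.7.1 words the antibody percent-binding model in the same way, and SAP 6.10 words the lead-in insulin dose model as "treatment-by-visit interaction in the model as fixed factors and patient as a random factor". None of these sections says anything about residual covariance.

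SAP 6.1 requires a change from the protocol's methods to be described and justified in the SAP and/or the CSR. The SAP contains no such statement about covariance.

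**The concern.** A mixed model with a random patient effect, nothing else random and independent residuals is a random-intercept model. It forces the same variance at every visit and the same correlation between every pair of visits. That is the structure which the protocol allows only after every richer one has failed to converge.

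This matters for a visit-specific contrast. Under the random-intercept model the Week 26 treatment difference gets a standard error built from the average of the visit variances, not from the Week 26 variance. Weight change from a fixed baseline may well spread out over 26 weeks. If it does, the Week 26 interval for objective 17 would be too short and its p-value too small, while the early-visit intervals would be too wide.

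**Working it through.** **Plan's own figure.** Neither document gives a design figure for weight. The only design calculation, for HbA1c, reproduces but does not bear on this point: SE = 1.1 × √(2/284) = 0.0923, 0.4/0.0923 − 1.96 = 2.37, power 99.1% against the stated figure of more than 99%.

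**Inputs.**
- Post-baseline weight visits in the treatment period (protocol Schedule of Activities): Weeks 2, 4, 8, 12, 18, 22 and 26.
- Patients per arm: 284 completers (protocol 10.1).
- SD of weight change at Week 26: 4 kg. This is an assumption; it sets the half-widths in kg and cancels from the ratio and the coverage.
- Growth of the SD over visits: an assumption, so a range is shown.

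**Formulas.** With balanced data, the random-intercept REML fit estimates the total variance as the mean of the visit variances, v̄, whatever the correlations. Then:
- Random-intercept SE at Week 26 = √(2v̄/n).
- Unstructured SE at Week 26 = √(2v₂₆/n).
- Ratio r = √(v̄/v₂₆).
- Coverage of a nominal 95% interval = 2Φ(1.96r) − 1.

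**Worked case, Week 26/Week 2 SD ratio of 2, SD linear in week.** The SDs are 2.00, 2.17, 2.50, 2.83, 3.33, 3.67 and 4.00 kg. The variances are 4.00, 4.69, 6.25, 8.03, 11.11, 13.44 and 16.00, with mean 9.08. So r = √(9.08/16) = 0.75 and coverage = 2Φ(1.476) − 1 = 86.0%.

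**Variance proportional to time.** The mean visit week is 92/7 = 13.14, so r = √(13.14/26) = 0.71 and coverage is 83.7%.

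**Range.** The unstructured half-width is 1.96 × 4 × √(2/284) = 0.658 kg in every row.

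| Week 26/Week 2 SD ratio | r | Random-intercept half-width (kg) | Coverage |
|---|---|---|---|
| 0.8 (falling) | 1.14 | 0.748 | 97.4% |
| 1.0 (constant) | 1.00 | 0.658 | 95.0% |
| 1.25 | 0.90 | 0.589 | 92.1% |
| 1.5 | 0.83 | 0.546 | 89.6% |
| 2 | 0.75 | 0.496 | 86.0% |
| 3 | 0.69 | 0.450 | 82.0% |
| Variance proportional to week (√13 ≈ 3.6) | 0.71 | 0.468 | 83.7% |

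The type I error is 100% minus the coverage.

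**Checks.** Simulation (3,000 runs per scenario) of the balanced-data interval gave coverage of 95.2%, 88.8%, 85.1% and 82.3% for ratios 1, 1.5, 2 and 3. The interval based on the Week 26 variance stayed between 94.5% and 95.3%. One random-intercept REML fit to simulated data at ratio 2 gave an SE of 0.250, against 0.333 from the Week 26 variance; 0.250/0.333 = 0.75, as the formula predicts.

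**The case against.** The best answer is that the SAP is silent rather than contrary. SAP 6.12.6 still calls the model an MMRM and nowhere says that visits share one variance. Protocol 10.3.1 already supplies a default for continuous longitudinal variables. The phrase may be shorthand for repeated measures within a patient: the lead-in insulin dose model in SAP 6.10 carries it, while the treatment-period dose model in 6.11.5 follows the HbA1c model, and nothing suggests that two covariance structures were intended for the same variable. A reader might infer that the sponsor deliberately replaced the unstructured covariance. The documents do not support that. No such decision is stated, and the SAP revision history mentions no covariance change, although it lists only the main changes between versions.

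This stands as to intent, but it does not make the text safe to program from. Coded as written, the model has one variance for all visits. A random patient intercept on top of an unstructured residual matrix would be over-parameterised, so the two statements cannot simply be combined.

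The objection also stands on consequence. Objective 17 is exploratory, and SAP 6.5 makes no multiplicity adjustment for it. SAP 6.12.6 also plans an ANCOVA of the last available treatment-period weight, which has no shared visit variance. That ANCOVA is only a partial substitute, because it mixes time points for patients who stop early, whereas the endpoint is the change to Week 26.

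**Conclusion.** SAP 6.12.6, 6.12.7.1 and 6.10 leave the covariance unstated. On a literal reading they conflict with protocol 10.3.1, and no justification is given.

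It is tempting to conclude that the Week 26 weight interval will be too narrow. The documents do not support that without a condition, because they give no SD of weight change at any visit. If the SD grows by a factor of 1.25 to 2 between Weeks 2 and 26, coverage under the literal model falls to between about 92% and 86%. Variance strictly proportional to time gives about 84%, but that is an extreme case, since it leaves no constant component for day-to-day or measurement variation. Constant variance gives no error, and falling variance gives an interval that is too wide. The figures assume balanced data.

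They apply to weight only. Nothing here sizes an effect for blood pressure, pulse, insulin dose or antibody binding, and a variable with stable variance would show little or none. No primary or multiplicity-adjusted conclusion depends on these models. Severity: minor.

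**What to change.** In SAP 6.12.6 (both the treatment-period and the lead-in models), 6.12.7.1 and 6.10, delete the random-factor wording. State instead that within-patient errors have an unstructured covariance, with the fallback order and Kenward-Roger degrees of freedom of SAP 6.11.1. If a random-intercept model was in fact intended, say so and give the justification that SAP 6.1 requires.

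For weight, seven visits mean 7 × 8/2 = 28 covariance parameters, which is modest with 284 completers per arm. The antibody model covers only patients with a treatment-emergent response, so the fallback order is more likely to be needed there.

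The cost is a sentence per section and the matching program statement. No data, visits or patients are involved.

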Study Period/Analysis	Patient Population	Baseline Observations	Post-Baseline Observations
1,5-AG	All Randomized Patients with a baseline and at least one post-baseline observation	Visit 8 prior to initiation of IP	Visits 11, 15, and 18 prior to discontinuation of IP AND Last of Visits 9-18 prior to discontinuation of IP
Health outcomes: ITSQ, EQ-5D-5L, EQ-VAS, WPAI-GH	All Randomized Patients with a baseline and a post-baseline observation	Last of Visits 1-8	Last of Visits 9-18 prior to discontinuation of IP
Safety Laboratory Tests (chemistry, hematology, lipids) – continuous analysis	All Patients in the Safety Population with a baseline and a post-baseline observation	Last of Visit 1-8	Visit 18 (planned) AND last of Visits 9-18 (planned including early discontinuation visits) regardless of IP use
Safety Laboratory Tests (chemistry, hematology, lipids) – categorical analysis	All Patients in the Safety Population with a normal baseline (with respect to the direction being analyzed) and a post-baseline observation	Visits 1-8 (including unplanned tests)	Visits 9-18 (including unplanned tests) regardless of IP use
TEAEs	All Patients in the Safety Population	Prior to first dose of randomized IP (or Visit 8 date if the dose date is missing) but after the first dose of open-label insulin lispro in the Lead-in Period	From first dose of randomized IP to last dose of randomized IP AND From first dose of randomized IP to Visit 801
Hypoglycemia events	Safety Population	All Visits 2-8	All Visits 9-18 prior to discontinuation of IP
Weight and vital signs	All Patients in the Safety Population with a baseline and a post-baseline observation	Last of Visits 2-8	Visits 9-18 prior to discontinuation of IP AND Visits 9-801 regardless of IP use
Anti-insulin lispro antibodies	Safety Population	Visit 2	Visits 3-801 regardless of IP use

Abbreviations: 1,5-AG = 1,5-Anhydroglucitol; ANCOVA = analysis of covariance; EQ-5D-5L = European Quality of Life - 5 Dimensions 5 Level; EQ-VAS = EuroQol visual analogue scale; HbA1c = hemoglobin A1c; IP = investigational product; ITSQ = Insulin Treatment Satisfaction Questionnaire; ITT = intention-to-treat; LOCF – last-observation-carried forward; MMTT = mixed meal tolerance test; MMRM = mixed-effect model repeated measures; PPG = postprandial glucose; SMBG = self-monitored blood glucose; TEAE = treatment-emergent adverse event; WPAI-GH = Work Productivity and Activity Impairment General Health.

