6.12.5. Clinical Laboratory Evaluation

The data from safety laboratory measures will be summarized at Week 26 where the lab test is planned to be collected. Postbaseline and change from baseline to postbaseline for laboratory tests will be summarized for patients who have both baseline and at least 1 post-baseline result and compared between treatment groups by using ANCOVA model with the term of treatment and baseline value of the response variable. Analyses will be provided in both SI and CN units.

The last nonmissing observation at or prior to Week 26 (planned tests including early termination) will also be analyzed by an ANCOVA model with the term of treatment, baseline value of the response variable.

The percentages of patients with treatment-emergent abnormal, high, or low laboratory results at any time during the treatment period (0 to 26 weeks) will be summarized for patients who have both baseline and at least 1 post-baseline result and compared between treatment groups using

Fisher's exact tests. A treatment-emergent abnormal result is defined as a change from normal at all baseline visits to abnormal at any time during the treatment period. A treatment-emergent high result is defined as a change from a value less than or equal to the high limit at all baseline visits to a value greater than the high limit at any time during the treatment period. A treatment-emergent low result is defined as a change from a value greater than or equal to the low limit at all baseline visits to a value less than the low limit at any time during the treatment period. Planned and unplanned measurements will be included. Covance reference ranges will generally be used to define the low and high limits. Only patients who have normal baseline values for the analysis being performed will be included in the analysis for treatment-emergence.

Liver enzymes measures will not be included in the above analyses as different analyses will be used as described in Section 6.12.4.4.2 and Section 6.12.4.4.3.

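### The denominator for treatment-emergent high or low vital signs keeps patients who cannot have the event, so the reported percentages are diluted by the share already beyond the limit at baseline (minor)

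*SAP*

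**What the plan says.** **Denominator for vital signs.** SAP 6.12.6 states that the percentages of patients with treatment-emergent high or low vital signs and weight "will be summarized by treatment group for patients who have both baseline and at least 1 postbaseline measurement". The weight and vital signs row of Table 6.2 (SAP 6.1) agrees: "All Patients in the Safety Population with a baseline and a post-baseline observation". Neither place requires a normal baseline.

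**Event definition.** SAP 6.12.6 defines a treatment-emergent high result as one that moves "from a value less than or equal to the high limit at all baseline visits to a value greater than the high limit", with a change criterion also met; low results mirror this. Table 6.7 sets the systolic criterion at "≥ 140 and increase from baseline ≥ 20" and the diastolic one at "≥ 90 and increase from baseline ≥ 10". Pulse also has absolute limits. Weight has only a percentage change. Arms are compared by Fisher's exact test.

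**Laboratory tests.** SAP 6.12.5 begins with nearly the same denominator wording, then adds: "Only patients who have normal baseline values for the analysis being performed will be included in the analysis for treatment-emergence". The categorical laboratory row of Table 6.2 repeats the restriction: "with a normal baseline (with respect to the direction being analyzed) and a post-baseline observation".

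**Baseline.** The vital-sign row of Table 6.2 takes the last value from Visits 2 to 8, a single reading. The event definition in 6.12.6 refers to all baseline visits.

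**The concern.** The event definition and the denominator do not match. A patient with one lead-in systolic reading above the limit can never become a case, whatever happens after randomization, yet counts as a patient without the event. The percentage no longer answers the usual question: of those who could newly cross the limit, how many did?

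The opening denominator sentence cannot be taken to imply an at-risk restriction. In 6.12.5 the SAP begins in the same way and then adds the restriction explicitly; in 6.12.6 it does not. A reader who compares the two safety tables would see the term treatment-emergent used over two kinds of denominator.

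The listed eligibility criteria set no blood pressure limit (protocol 6.1 and 6.2), so patients with high readings can be randomized. LY900014 contains a vasodilator excipient (protocol 3.2), so the blood pressure table will be read with some interest.

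**Working it through.** The documents state no baseline blood pressure distribution and no expected event rate, so there is no planned figure to reproduce.

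**Step 1. Size of the dilution.** Let f be the share of patients beyond the limit at baseline, and r the event rate among the rest.

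- Reported percentage = r × (1 − f).
- Relative understatement = [r − r(1 − f)] / r = f.
- Absolute difference between arms with equal f = (r₁ − r₂)(1 − f), also smaller by f.
- Risk ratio = r₁(1 − f) / [r₂(1 − f)] = r₁ / r₂, unchanged.
- Correction factor 1/(1 − f): 1.11 at f = 10%, 1.25 at 20%, 1.67 at 40%, 2.0 at 50%.

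**Step 2. Plausible f (all distributions assumed).** Patient means and visit-to-visit errors are taken as normal. Under the protocol's Schedule of Activities, the vital-sign readings between Visits 2 and 8 fall at Visits 2, 5, 7 and 8. Hence f is shown for one reading (Table 6.2) and for any of four (6.12.6).

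| Category | Assumed mean | Assumed SD between / within patients | f, one reading | f, any of four |
|---|---|---|---|---|
| Systolic above 140 mm Hg | 124 to 136 | 11/8 to 13/9 | 11% to 39% | 25% to 63% |
| Diastolic 90 or more | 74 to 80 | 8/6 | 6% to 17% | 15% to 36% |
| Systolic 90 or less | 126 to 134 | 13/9 | not needed | 1% to 4% |
| Pulse above 100 | 76 | 9/5 | not needed | 2.3% |
| Pulse below 50 | 76 | 9/5 | not needed | 1.4% |
| Weight | none | none | 0% | 0% |

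Weight is zero because it has no absolute limit. Table 6.7 counts a systolic reading of exactly 140 as high, while the definition in the text requires a value above the limit. Using 140 or more instead adds about 1 to 3 percentage points to the systolic row.

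**Step 3. Effect on the comparison.** Take 335 patients per arm (670/2), f = 35%, and assumed at-risk rates of about 25% and 17%. Then 218 per arm are at risk, with 54 and 37 events.

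| Denominator | Rates | Difference | Risk ratio | Fisher p |
|---|---|---|---|---|
| All patients (335) | 16.1% vs 11.0% | 5.1 points | 1.46 | 0.071 |
| At risk (218) | 24.8% vs 17.0% | 7.8 points | 1.46 | 0.059 |

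At f = 20% p moves from 0.039 to 0.034, and at f = 50% from 0.132 to 0.108.

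**Step 4. Which baseline the change is measured from.** Table 6.7 asks for an increase from baseline without saying which value that is. Assume systolic means of 128 to 136, SDs of 11/8 to 13/9, four baseline readings that must all be within the limit, and seven post-baseline readings.

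- Change from the last baseline reading: event rates of about 4% to 6% of all patients, or 7.5% to 14.4% of those at risk.
- Change from the highest baseline reading: about 0.6% to 1.3%, or 1.2% to 3.3%.

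The ratio between the two denominators is the same either way, but the level of the reported rate is not.

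**The case against.** Several arguments on the other side stand.

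- Randomization should make f similar in the two arms. The risk ratio is then untouched and the Fisher result moves little (step 3). No conclusion of the trial is shown to change.
- SAP 6.12.6 also plans repeated-measures models by visit, analysis of covariance of the last observation, and maximum-to-maximum and minimum-to-minimum changes. These cover patients already high at baseline and do not use this denominator.
- Vital signs belong to a tertiary/exploratory objective, with no multiplicity adjustment.
- The laboratory and vital-sign definitions are not identical, because vital signs add a change criterion. Nor does the SAP have one rule for all laboratory tests: liver enzyme elevations (6.12.4.4.3) are summarized over all patients with a post-baseline value, but by baseline category. That stratification shows who started high; the vital-sign table neither restricts nor stratifies.
- The Table 6.2 vital-sign row is not split into continuous and categorical analyses as the laboratory rows are. It may have been written for the continuous models, and so is weak evidence of a deliberate choice of denominator. The sentence in 6.12.6 itself does not have this excuse.

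A reader might infer that new high blood pressure is understated by about half. The documents do not support that as a statement of fact. It needs f near 50%, which is reachable under the assumptions only for high systolic pressure with several baseline readings counted. It is not reached for systolic pressure with one reading, or for diastolic pressure at all. A reader might also infer that a true difference between arms is masked; only the absolute difference shrinks.

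**Conclusion.** The mismatch is established from the text alone: the denominator includes patients whom the event definition rules out, and the laboratory analysis removes them. The reported percentages are understated by exactly f.

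The size of f is an assumption, not a figure from the plan. It matters mainly for high systolic pressure, less for high diastolic pressure, and hardly at all for the low-systolic and pulse categories; weight is unaffected. Equal f in the two arms is expected from randomization but not guaranteed.

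Severity: minor. It affects how one safety table reads and how it compares with the laboratory table, not the trial's conclusions.

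**What to change.** In SAP 6.12.6 and the vital-sign row of Table 6.2, for the blood pressure and pulse categories:

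1. Add the laboratory rule: include only patients not beyond the limit, in the direction analysed, at all baseline visits, who also have a post-baseline value.
2. Show that number as the denominator for each category and arm.
3. Reconcile the single last value of Visits 2 to 8 in Table 6.2 with the all-visits wording in 6.12.6, and state which baseline value the change criterion in Table 6.7 uses. In the same edit, settle whether a reading exactly at a blood pressure limit counts as beyond it.

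Leave weight as it is. If the programs already restrict the denominator, the text only needs to say so.

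The cost is one or two SAP sentences, one table row and a denominator change in one output. No data collection or clinical procedure changes.
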